**5. Upload any supporting tables or documents:**

ID: HM20005575

View: SF - Study Activities

## Study Activities

**1. \* Select which study type best describes the majority of the study. Your response will help determine which IRB panel should review this.**

Bio-Medical

Qualitative - Social/Behavioral/Education (SBE)

Quantitative - SBE

Mixed Method - SBE

Mixed Method - Biomedical

**2. \* This study will involve (check all that apply):**

procedures such as surveys, interviews, field studies, focus groups, educational tests, deception, psycho-physiological testing, any other similar data collection

secondary data analysis: procedures such as analysis of information collected for non-research purposes (includes both retrospective and prospectively collected information), or analysis of data previously collected for a prior research study

drugs, devices, experimental interventions, biohazards, radiation, other medical or surgical procedures

ID: HM20005575

View: SF - Bio-Med Project Details

## Bio-Med Project Details

**1. \* Select all details that apply:**

Drugs, Biologics, Supplements, and/or Other Compounds

Placebo

Washout Period

**Device Evaluation**

Bio-Hazards, Other Toxins, Recombinant DNA/Gene Transfer

Radiation Exposure and/or Scans involving radiation (PET, MRA)

Stem Cells

Expanded Access - Treatment Use of an Investigational Product

Other Medical or Surgical Procedures

**Protected Health Information (PHI)**

ID: HM20005575

View: SF - Bio-Med Device Evaluation Details

## Bio-Medical Device Evaluation Details

1. \* Select the type of device evaluation this study will involve:

**Marketed Medical Device (including 510k device)**

Investigational Medical Device

New Use for Marketed Medical Device

Other Devices

2. \* List devices this study will involve:

Device	Manufacturer	IDE	IDE Holder	Doc
Servo-i Ventilator	Maquet	N/A	Not Required	Servo-i (0.01)
Servo-i NAVA	Maquet	N/A	Not Required	NAVA brochure(0.01)

3. \* Documents required for upload:

■ If the IDE is held by a sponsor-investigator, upload at least one of the following documents for verification of the IDE number:

- Study Protocol including IDE number
- Communication from the FDA with verification of the IDE

■ If the IDE is held by the sponsor, upload at least one of the following documents for verification of the IDE number (required if IND held by sponsor):

- Sponsor protocol
- Communication from the sponsor verifying the IDE number
- Communication from the FDA verifying the IDE number

■ If evaluating an approved device, upload documentation of the approved use(s).

ID: HM20005575

View: SF - Data Collection Details

## Data Collection Details

1. \* Select all involved in the study:

Specimen/Biologic Sample Collection

**Protected Health Information (PHI)**

Audio/Video

Existing Data or Specimens Not From a Registry or Repository

Use of Internet for Data Collection

Registries/Repositories (Includes Accessing, Contributing or Creating)

None of the Above

2. \* Select all identifiers that will be collected as part of this study (including for recruitment, data gathering, data analysis, etc.), even if the data will eventually be anonymized:

Names

Geographic Locators Below State Level

Social Security Numbers

**Dates (year alone is not an identifier)**

Ages >89

Phone Numbers

 Facsimile Numbers
 E-mail Addresses
 Medical Record Numbers
 Device Identifiers
 Biometric Identifiers
 Web URLs
 IP Addresses
 Account Numbers
 Health Plan Numbers
 Full Face Photos or Comparable Images
 License/Certification Numbers
 Vehicle ID Numbers
 Other Unique Identifier
 No Identifiers
 Employee V#

3. If "Other Unique Identifier" was selected above, describe the identifiers:

4. \* Will participants be able to withdraw their data (paper, electronic, or specimens) from the study if they no longer wish to participate:

Yes  
 No

5. If yes above, describe how participants will be able to withdraw their data:

ID: HM20005575

View: SF - HIPAA

## HIPAA

1. \* Describe the protected health information that will be obtained or used in this research:

MRN, birth dates, date of study. The only data that are needed from the EMR are: gestational age, birth-weight, age at study, medications while on study, ventilator mode and settings at time of study, gender and Apgar scores and head ultrasound results.

2. \* Describe the source(s) of the protected health information:

VCU's electronic medical record system

3. \* Explain how the PHI collected or used in this research is the minimum necessary to accomplish this research:

The above mentioned data will be needed to evaluate the role of maturity on the outcomes. These variables are either standard clinical descriptors of a neonatal research population (birth-weight, gestational age, gender, Apgar Scores) to inform any reader of an aggregated data publication about whether the study sample is representative of the relevant population, or ones that can influence the outcome variable (medications, ventilator history, evidence of brain bleeds)

4. \* Select all pathways this research will employ to use or access PHI:

 De-Identified Data
 Limited Data Set
 Waiver of Authorization
 Partial Waiver of Authorization
 Signed Authorization Combined with Consent Form
 Signed Authorization as Stand-Alone Form

ID: HM20005575

View: SF - Data Confidentiality and Storage

Destroyed at the end of study once the minimum time required for data retention has been met per VCU Data Retention Policy and/or sponsor retention requirements

Destroyed when notified by sponsor but not less than the minimum time required for data retention per VCU Data Retention Policy

Other

7. If Other, explain:

8. If "stored indefinitely with identifiers attached", explain why identifiers are necessary:

ID: HM20005575

View: SF - Types of Sites

## Types of Sites

1. \* Select which of the following accurately describes this study:

Not Multicenter Study

Multicenter Study - VCU Lead

Multicenter Study - Non-VCU Lead

2. \* Select all sites where study interventions or interactions will occur and/or identifiable data will be held:

VCU Site

Non-VCU Site (VCU Investigators are conducting/overseeing the conduct of the study)

3. \* Is there a community partner in this research study:

Yes

No

ID: HM20005575

View: SF - VCU Site Details

## VCU Site Details

1. \* Select all VCU sites that will be utilized in this study:

Clinical Research Services Unit (CRSU)

Massey Cancer Center

VCU Health System

VCU Qatar

Other VCU Site

2. \* Provide details regarding each VCU Site including:

- what clinics / facilities will be used

- resources that are available for the conduct of this study:

Site - NICU on CCH6

Study involves normal care practices - normal care and monitoring by personnel will continue during the study period.

ID: HM20005575

View: SF - VCU Health System

## VCU Health System

1. \* The PI has reviewed and agrees to comply with the Conduct of Clinical Research in VCU Health System Patient Care Areas policy:

Yes

No

2. \* Explain how you will notify and obtain support from patient care providers in the units where the study will be conducted:

Investigators will brief and inform clinical personnel of study design by poster in break room, email and personal interactions before first enrollment.

ID: HM20005575

View: SF - Study Funding

## Study Funding

1. \* Have you applied for funding:  
 Yes  
 No

2. If so, is this study already funded:  
 Yes  
 No

ID: HM20005575

View: SF - Study Population

## Study Population

1. \* Provide the total number of participants you expect to enroll in this study under the VCU IRB:  
15

2. If this is a multi-Center Project, what is the total anticipated number of subjects across all sites:

3. \* Provide justification for the sample size:

Sample Size

Based on published data, monitored events occur at an average frequency of 9.2 over a 4-hour period. The degree of variability is not known but assuming an SD of 50%, a sample size of 10 subjects would have an 0.8 power for a 50% reduction in events at an alpha of 0.05. A similar study to ours comparing NIPPV and flow-synchronized NIPPV (2) had 19 participants and achieved statistically significant differences between the two modalities. Based on this, we are anticipating a need for 15 subjects

4. \* List the study inclusion criteria:

1. < 1501 grams (VLBW infant)
2. Patient must be receiving daily caffeine therapy for apnea
3. On non-invasive ventilation, either NIPPV or non-invasive NAVA

5. \* List the study exclusion criteria:

1. No concerns for acute sepsis (i.e., blood cultures, if drawn, have been negative for 48 hours, and no active signs/symptoms of sepsis).
2. No history of meningitis or seizures
3. No signs of increased intracranial pressure, including bulging fontanelle, presence of ventricular shunt device, or ventriculomegaly by most recent ultrasound.
4. Presence of Grade III or IV intraventricular hemorrhage
5. No cyanotic heart defects or clinically significant congenital heart disease. Will allow PDA, PFO, and mild to moderate ASD/VSD as determined by pediatric cardiology.
6. Non-English speaking legal representatives (parents)

6. \* Check all participant groups that are likely to be involved in this study. If it is possible that a regulated vulnerable population (children, pregnant women, prisoners) COULD BE involved in the study, be sure to check them:

Healthy Volunteers

Children

Emancipated Minors

Pregnant Women

Fetuses, Neonates, Fetal Material or In-Vitro Fertilization

Prisoners

Decisionally Impaired Adults

When cancer is integral to the research - cancer Patients, Family Members, Healthcare Providers or Prevention

VCU Health System Patients

Non-VCU Patients

VCU/VCUHS Students or Trainees

VCU/VCUHS Employees

Individuals with Limited English Proficiency

Active Military Personnel

When researching in a K-12 environment - populations Within School Districts or Other Learning Environments

7. If you are either targeting, or excluding, a particular segment of the population / community, provide a description of the group/organization/community and provide a rationale:

The decreased ability to explain the technical aspects of the study to LEP parents through either medically-approved translation service or a medically-certified informed consent form in other languages makes it difficult for these parents to be fully informed to make a decision in the best interests of their child.

8. \* Select the age range(s) of the participants who may be involved in this study:

< 1 Year

1 - 6 Years

7 - 12 Years

13 - 17 Years

18 - 20 Years

21 - 65 Years

> 65 Years

ID: HM20005575

View: SF - Children

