## Research Description

1. \* Describe the study hypothesis and/or research questions. Use lay language whenever possible.

We hypothesize that in very low birth weight infants who require respiratory support via noninvasive ventilation, that synchronizing the ventilator breath with the baby's breath using neurally adjusted ventilatory assist (NAVA) will reduce the number and/or severity of apnea/bradycardia/desaturation episodes compared to nasal intermittent positive pressure ventilation (NIPPV).

2. \* Describe the study's specific aims or goals. Use lay language whenever possible.

The specific goal is to measure the number and severity of cessation of breath/low heart rate/low blood oxygen level events (ie, apnea/bradycardia/desaturation events) in a 4 hour period while receiving one of the two types of non-invasive ventilation modes (either NIPPV or NAVA) currently used in very low birthweight infants.

3. \* Describe the study's background and significance, including citations, or upload a citation list in document upload. Use lay language whenever possible.

Very low birthweight (VLBW) premature infants in the NICU frequently require respiratory support for prolonged periods of time. Invasive mechanical ventilation (which requires intubating the baby with a tube to provide breaths) can lead to ventilator-induced lung injury. Because of this, noninvasive respiratory support has become increasingly popular, as this form of ventilation has been shown to reduce the incidence of permanent lung injury. (1)

There are several methods to provide non-invasive support. The gentlest is continual flow of air and oxygen via nasal cannula. However, premature infants often develop apnea, either because the signals from their immature brain are not yet sufficient or because the muscles in the back of their throat do not get enough nerve signals to maintain sufficient opening. As a result, babies on nasal cannula often develop clinical apnea/bradycardia/desaturations. Before putting these babies back on invasive ventilation, clinicians often try to provide the baby with machine breaths while still on non-invasive ventilation. This method is called nasal intermittent positive pressure ventilation and studies have demonstrated that this method reduces the need for re-intubation in VLBW infants (1) and reduces the rate of apneic events.

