Analysis: The simultaneous recordings will be scored for: a) Apnea (cessation of breath resulting in no airflow for > 20 seconds or for > 5 seconds if accompanied by bradycardia [HR < 100 bpm] or desaturation [Oximetry < 85%]) b) Bradycardia (hr < 100 bpm for > 5 seconds) c) Desaturation (< 85% for > 5 seconds) d) Synchronicity, measured as average triggering and cycling-off delays for each modality, and total wasted patient respiratory efforts for each modality.

Primary outcome: The number of isolated apneas, bradycardias and desaturations and the number of combined events will be compared by mode of ventilation.

Secondary outcome: a) Synchronicity from the ventilator at the time of an event. This will be analyzed to determine whether asynchronicity is related to increased number of events during the study. b) Overall asynchronicity counts will be determined by ventilator data that can be uploaded and analyzed with software supplied by the manufacturer. c) average mean airway pressure and peak inspiratory pressures required in each mode of ventilation.

There are no well-characterized tools to measure premature infant 'comfort'. There are semi-subjective pain scores that the nursing staff use but we are more likely to have irritation or discomfort from the probe. Thus, this will be an ongoing assessment of a) the infant's state - quiet sleep, quiet awake, agitated, restless, etc. b) new onset tachycardia or tachypnea coincident with applying the probes. c) facial grimaces that are different than baseline as assessed by the nurse caring for the patient

The threshold for an adverse event will be dependent on the baseline level. If the baseline rate is, say, 4-6 events an hour, a 25% increase is 1 event, which is within the patient's variance. On the other hand, in one having no events, just one event is a 100% increase. We have 2 criteria - 1) An event that requires intervention with breathing support such as with more breaths or a bag and mask, 2) an increase from baseline of at least 4-5 events/hr. from baseline

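### Several primary event counts are declared with no deciding count, test or multiplicity rule, while power is stated for one event count not explicitly matched to any of them

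*Combined protocol and SAP*

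**What the plan says.** The primary outcome is in the Research Description, item 4: "The number of isolated apneas, bradycardias and desaturations and the number of combined events will be compared by mode of ventilation". That sentence is also the whole analysis statement for the primary outcome. Item 4 gives scoring rules for apnea, bradycardia and desaturation, but defines neither an isolated event nor a combined event.

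The sample size is in Study Population, item 3. It starts from one published rate: "monitored events occur at an average frequency of 9.2 over a 4-hour period". It continues "The degree of variability is not known but assuming an SD of 50" per cent, and concludes that "a sample size of 10 subjects would have an 0.8 power for a 50% reduction in events at an alpha of 0.05". After a comparison with a similar study of 19 participants it adds "Based on this, we are anticipating a need for 15 subjects". It does not say which events make up the 9.2. It also does not say whether the standard deviation (SD) is that of the within-infant difference or of the count in one mode.

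The hypothesis in item 1 of the Research Description is that synchronized ventilation "will reduce the number and/or severity of apnea/bradycardia/desaturation episodes", and the aim in item 2 reads "The specific goal is to measure the number and severity of cessation of breath/low heart rate/low blood oxygen level events". No measure of severity is defined.

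**The concern.** A stated alpha of 0.05 and a stated power of 0.8 each belong to one test of one quantity. Here the quantity that is powered and the quantities declared primary are described in different terms, and nothing links them.

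Two things are at stake. First, if each count is tested at 0.05 and a favourable result on any of them is taken as the answer, the overall false-positive rate exceeds 0.05. Second, if the counts disagree, the plan gives no rule for which one answers the study question, and a choice made after the data are seen offers no protection. A reader also cannot tell which comparison the 0.8 power describes, or whether it applies to a rarer component count at all.

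**Working it through.** **Inputs from the documents.** Mean 9.2 events per 4 hours; SD 50% of the mean, 0.5 × 9.2 = 4.6; effect a 50% reduction, also 4.6; alpha 0.05; n = 10 for the power statement and 15 planned (all Study Population, items 1 and 3). Each infant is recorded for 4 hours on each mode, so the natural comparison is paired (Research Description, item 4).

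**Reproducing the stated figure.** For a paired t-test the standardized effect is d = difference / SD of differences, and power comes from the noncentral t distribution with n − 1 degrees of freedom and noncentrality d√n.

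- If 4.6 is the SD of within-infant differences, d = 4.6/4.6 = 1.0. At n = 10 the noncentrality is 3.16 and two-sided power at 0.05 is 0.803. The stated 0.8 is reproduced. At n = 15 power is 0.949.
- A one-sided test would give 0.898 at n = 10, so the stated figure fits a two-sided paired test.
- An unpaired normal approximation with SDs of 4.6 and 2.3 in the two modes also fits: 4.6/√((4.6² + 2.3²)/10) − 1.96 = 0.87, power 0.807.

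Two different analyses give the same 0.8, so the figure does not reveal which was intended.

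**False-positive rate if any count may decide.** This decision rule is an assumption; the plan states none. With independent counts each at 0.05, the rate is 1 − 0.95² = 9.75% for two and 1 − 0.95⁴ = 18.5% for four. Counts from the same infants will be correlated and the documents give no correlation, so a range is shown. It was simulated with paired t-tests, n = 15, equally correlated normal differences and 200,000 runs:

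| Correlation | Two counts | Four counts |
|---|---|---|
| 0 | about 9.8% | about 18.5% |
| 0.5 | about 9.1% | about 15.9% |
| 0.8 | about 8% | about 12% |
| 0.95 | about 6.6% | about 8.2% |

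If every count had to succeed, the rate would not exceed 5%. With independent counts and d = 1.0 for each, power at n = 15 would then be 0.949² = 0.90 (two) or 0.949⁴ = 0.81 (four).

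**Power per count with Bonferroni (alpha 0.05/k), d = 1.0 for every count:**

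| Counts | Alpha | n = 10 | n = 15 |
|---|---|---|---|
| 1 | 0.05 | 0.80 | 0.95 |
| 2 | 0.025 | 0.68 | 0.90 |
| 4 | 0.0125 | 0.55 | 0.82 |

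**If 4.6 is instead the SD within each mode.** With zero correlation between modes, the SD of differences is 4.6 × √2 = 6.5 and d = 0.71. Power at n = 15 is then 0.72 for one count, 0.60 for two and 0.48 for four with Bonferroni. With correlation 0.5 between modes, the SD of differences is again 4.6 and the table above applies.

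**The case against.** The strongest reply is that the intended count can be inferred. Items 1 and 2 of the Research Description speak of apnea/bradycardia/desaturation events as one class, and the aim sets a 4-hour window. The sample-size section then powers events over 4 hours. The natural reading is the overall count, and if combined events means the pooled total, the powered count is one of the declared ones. This stands in part: a reader might infer that the power belongs to none of the declared counts, and the documents do not support that. They support only that the match is not explicit, because combined could equally mean co-occurring events.

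A second tempting inference comes from the apnea definition, "cessation of breath resulting in no airflow for > 20 seconds or for > 5 seconds if accompanied by bradycardia" or desaturation: that a pause of 5 to 20 seconds can never be an isolated apnea, so the counts must measure different things. That follows only if isolated means unaccompanied, and the term is not defined. The point does not need it.

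Third, the inflation depends on a rule the plan does not state. Under an all-counts rule there is none, and with highly correlated counts it is small. The percentages are illustrations, not the trial's error rate.

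Fourth, at the planned 15 infants even a four-way Bonferroni split leaves 0.82 power under the plan's own standardized effect, so a reader should not infer that the study is underpowered. That reassurance is itself conditional: it needs every component count to share the same relative SD and the same 50% reduction, and no component means or SDs are given.

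Finally, this is an IRB application in lay language for a small single-centre crossover study, where formal multiplicity control can seem excessive. But the plan labels a primary outcome, claims power at a stated alpha, and in its statement of scientific benefit expects the analysis may determine which mode is better. Naming the deciding count is a modest requirement for that.

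**Conclusion.** The point holds in limited form. The plan declares two to four primary counts without a deciding count, a test or a multiplicity rule, and its power statement concerns one count not explicitly matched to any of them. The sample-size arithmetic is not wrong: 10 infants give 0.80, and 15 give 0.95, for a single count with mean 9.2, a 50% reduction and an SD of within-infant differences of 4.6, tested two-sided by a paired t-test.

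Beyond that case the size depends on unstated choices. Under an any-count rule at 0.05 each, the false-positive chance is about 7-10% (two counts) or 8-18.5% (four) over correlations from 0.95 to 0; under an all-counts rule it is not inflated. Bonferroni power at n = 15 runs from 0.90 (two counts) to 0.82 (four) with d = 1.0 throughout. If the 4.6 is a within-mode SD with no correlation between modes, it is 0.60 to 0.48, and 0.72 for a single unadjusted count. This should be settled before analysis; it does not invalidate the design.

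**What to change.** Before analysis:

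- Name one primary count. The best candidate is the total of apnea, bradycardia and desaturation events per 4-hour recording, since the sample-size section appears to power it. Define how overlapping signals are counted, and define isolated and combined.
- Compare that count between modes by one paired (crossover) test at two-sided 0.05, and name the test.
- Make the isolated and co-occurring counts secondary, reported with confidence intervals. If several counts stay primary, state the multiplicity rule, or that all must succeed, and give the resulting lower power.
- State which events the published 9.2 counted and what the 50% SD refers to. Restate power conditionally for the named count: 0.80 (n = 10) or 0.95 (n = 15) if its mean is 9.2 and its SD of within-infant differences is 4.6.

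The cost is a wording change and one recalculation, with no extra infants or data. The downside is that the other counts become descriptive, and the restated power may be lower if the named count is rarer or more variable than assumed.
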